6.4. DLT EVALUABLE ANALYSIS SET (DEAS)

The DLT Evaluable Analysis Set (DEAS) is defined as all patients enrolled in the dose escalation phase of the study who are evaluable for DLT assessment. A subject is DLT evaluable if he/she meets the following criteria:

 has received at least 75% of the assigned dose of study medication during the DLT assessment window

OR

has not completed the DLT assessment period due to a DLT

DLT assessment window is defined as the treatment period of 28 days (i.e., from Cycle 1, Day 1 [the day of the first administration of treatment] through Cycle 1, Day 28).

7. GENERAL CONSIDERATIONS

7.1. REFERENCE START DATE AND STUDY DAY

Study Day will be calculated from the reference start date and will be used to show start/stop day of assessments and events.

Reference start date is defined as the day of first non-zero administration of treatment, and will appear in every listing where an assessment date or event date appears.

If the date of the event is on or after the reference date, then:

Study Day = (date of event – reference date) + 1.

If the date of the event is prior to the reference date, then:

Study Day = (date of event – reference date).

In the situation where the event date is partial or missing, the date will appear partial or missing in the listings. Study day and any corresponding durations will be presented based on the imputations specified in section 7.10 Missing Data, but presented as missing in the listings.

7.2. BASELINE AND CHANGE FROM BASELINE

Unless otherwise specified, baseline is defined as the last non-missing measurement taken within 21 days prior to the day of first non-zero administration of treatment (including

unscheduled assessments). Bone marrow biopsy and/or aspirate are done at baseline or up to 3 months before of the Cycle 1 Day 1. In the case where the last non-missing measurement is taken on the day of first non-zero administration of treatment without time point collected, that measurement will be considered baseline. For Electrocardiogram (ECG) parameters, last assessment performed prior to or on first non-zero dose date with time point marked as "pre-dose" will be considered as baseline. Adverse Events (AEs) and medications commencing on the day of first non-zero administration of treatment will be considered post-baseline.

For quantitative measurements, change from baseline (CFB) will be calculated as:

CFB = Assessment value at each visit – Baseline value.

Percentage CFB (% CFB) is to be calculated as:

% CFB = (Assessment value at each visit – Baseline value)/Baseline value × 100.

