5.7.11 Electrocardiogram

All electrocardiograms (ECGs) are required to be performed using a 12-lead tracing. ECG measurements will include PR interval, QRS interval, RR interval, QT/QTcF interval, and heart rate.

For dose escalation stage, triplicate ECGs, approximately 2 minutes apart, should be performed at screening, pre-dose, and 2 ± 0.5 and 4 ± 0.5 hours post-dose on Days 1 and 15 of Cycle 1 in order to evaluate concentration-QT relationship with HMPL-689. Single ECG will be conducted at any time on Day 1 of every cycle from Cycle 2 and onwards, and at study completion or early termination. For dose expansion stage, ECGs should be collected according to the schedule and time points in [Appendix 3](#).

Additional ECGs and other cardiac monitoring will be provided as clinically indicated during the study.

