7.3.5 Pharmacodynamics (Electrocardiogram) Analysis

Patients who 1) receive at least 1 dose of study drug and 2) have baseline and at least 1 postdose ECG measurement will be evaluable for pharmacodynamic (ECG) evaluation. Patients who had reduced dosage, prolonged dose interruption of >2 days in cycle 1, any dose interruption within 3 days before Cycle 1 Day 15, or were discontinued from the study prior to the completion of ECG data collection (Cycle 1 Day 15) will be excluded. For each of the ECG parameters, the average values from the 3 readings of a triplicate ECG set will be used in the analysis.

For all ECG parameters, the baseline will be defined as the mean values of the triplicate ECG measurements taken at predose on Cycle 1 Day 1.

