7.3.5.1 Corrected QT Intervals

The terminology QTc is used in this section as a general notation for QTc using any of the specified methods.

The QT interval data will be corrected for heart rate using 2 correction methods (QTcF and corrected QT interval by Bazett – QTcB). For each QTc correction method, the relationship between QTc and RR at baseline will be evaluated graphically by plotting the logarithm of baseline QTc values against the logarithm of corresponding RR intervals. QTcF will be used as the primary correction method for statistical analysis. If the correlation between QTc and RR intervals remains significant using the Fridericia correction method, an alternative correction method may be considered for statistical analysis in addition to QTcF.

For the statistical analysis based on the primary correction method (QTcF), the mean changes from baseline (Δ QTc) at each time point will be summarized (mean, standard deviation, median and

range, and 2-sided 90% CI). Mean values for the difference and 2 sided 90% CI for mean difference will be calculated at each time point.

The primary analysis will focus on the maximum mean change from baseline in QTc (Δ QTc) on Cycle 1 Day 15, which will be estimated by the mean QTc change at around t_{max} , the time when the C_{max} is reached (i.e., steady state). The same analysis will be performed for Δ QT data using other correction methods if data warrant. The mean change from baseline in QTc (\pm standard deviation) over time will be plotted.

In addition, QTc will be categorized based on International Council for Harmonisation (ICH) E14 guidelines. Tables will present the number and percentage of patients meeting or exceeding the following categories:

- QTc prolongation:
 - Absolute values >450 to ≤ 480 msec
 - Absolute values >480 to ≤ 500 msec
 - Absolute values >500 msec
- QTc change from baseline:
 - Increase from baseline >30 to ≤ 60 msec
 - Increase from baseline >60 msec

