7.5. RETESTS, UNSCHEDULED VISITS AND EARLY TERMINATION DATA

In general, for by-visit summaries, data recorded at the nominal visit will be presented. Unscheduled measurements will not be included in by-visit summaries but will contribute to the worst-case value where required (e.g. shift table).

In the case of a retest (same visit number assigned), the latest available measurement for that visit will be used for by-visit summaries.

Listings will include scheduled, unscheduled, retest visits, and early discontinuation data.

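### The SAP takes the last pre-dose ECG assessment as baseline and has no averaging rule, which conflicts with the protocol's mean of the Cycle 1 Day 1 pre-dose triplicate

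*SAP*

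**What the plan says.** **Protocol.** Section 7.3.5 applies one rule to every ECG parameter: "the baseline will be defined as the mean values of the triplicate ECG measurements taken at predose on Cycle 1 Day 1". For triplicate time points generally, "the average values from the 3 readings of a triplicate ECG set will be used in the analysis". Section 5.7.11 gives the dose-escalation schedule: "triplicate ECGs, approximately 2 minutes apart, should be performed at screening, pre-dose", and again 2 and 4 hours post-dose on Days 1 and 15 of Cycle 1. After that the design changes: "Single ECG will be conducted at any time on Day 1 of every cycle from Cycle 2 and onwards". Section 7.3.5.1 then plans the QTc analysis: mean change at each time point with a 90% CI, and categories of absolute value and of increase. "The primary analysis will focus on the maximum mean change from baseline in QTc" on Cycle 1 Day 15.

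**SAP.** Section 7.2 has a sentence specific to ECG. It takes as baseline the "last assessment performed prior to or on first non-zero dose date with time point marked as" pre-dose. Section 7.5 says that for a retest carrying the same visit number, "the latest available measurement for that visit will be used for by-visit summaries". Section 17.5 names the ECG parameters, says that central readings will be reported, and ends with a listing. It contains no averaging rule, no summary of change and no category table. The effect on cardiac repolarization is nevertheless a secondary objective in SAP 3.2.

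**The concern.** The two documents define the same quantity differently. Protocol 7.3 leaves analysis detail to the SAP, and the SAP introduction sends only pharmacokinetics to a separate plan, so a programmer would follow SAP 7.2. If that yields one tracing, two of the three baseline readings go unused. The replicate error of the remaining one then enters every change calculated for that patient. Because the error is shared, one low tracing raises all of that patient's changes together.

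At stake are the precision of the mean QTc change in Stage 1 cohorts, whose minimum size is 3, and the counts of patients in the protocol's change categories, the highest of which is "Increase from baseline >60 msec".

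**Working it through.** **Step 1: which records the SAP rule leaves.** In dose escalation, the ECGs up to the first dose are the screening triplicate and the Cycle 1 Day 1 pre-dose triplicate (protocol 5.7.11). The Day 15 pre-dose set falls after the first dose date. Restricting to records marked pre-dose on or before that date therefore normally leaves only the Day 1 triplicate, and *last* has little to do except choose among its tracings. If *assessment* means the whole set, the SAP still does not say how three values become one.

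**Step 2: model.** The documents give no QTc sample size, SD or outlier rate, so there is no stated figure to reproduce. I write a reading as true value + time-point component (SD s_t) + replicate component (SD s_e), with independent components. Both SDs are assumptions. The SD of change is then:

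- triplicate mean at both times (protocol): √(2s_t² + 2s_e²/3)
- single baseline, triplicate-mean post-dose: √(2s_t² + s_e² + s_e²/3) = √(2s_t² + 4s_e²/3)

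**Step 3: ratio of the two SDs.**

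- s_t = 0 (the ceiling): √((4/3)/(2/3)) = √2 = 1.41
- s_e = s_t: √((2 + 4/3)/(2 + 2/3)) = √1.25 = 1.12
- s_e = s_t/2: √((2 + 1/3)/(2 + 1/6)) = √1.077 = 1.04

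**Step 4: false increases above 30 msec.** This is the normal upper tail with no true change, per comparison.

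| s_t, s_e (msec, assumed) | SD, protocol | SD, single baseline | Ratio | >30 msec, protocol | >30 msec, single baseline |
|---|---|---|---|---|---|
| 0, 8 | 6.5 | 9.2 | 1.41 | <0.001% | 0.06% |
| 6, 8 | 10.7 | 12.5 | 1.17 | 0.25% | 0.84% |
| 8, 8 | 13.1 | 14.6 | 1.12 | 1.1% | 2.0% |
| 8, 4 | 11.8 | 12.2 | 1.04 | 0.54% | 0.71% |
| 10, 10 | 16.3 | 18.3 | 1.12 | 3.3% | 5.0% |
| 12, 6 | 17.7 | 18.3 | 1.04 | 4.5% | 5.1% |

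The largest rise is 5.0 − 3.3 = 1.7 percentage points. False increases above 60 msec stay at about 0.05% or less with a single baseline in every case tried.

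**Step 5: Cycle 2 onward in escalation.** The post-dose ECG is single by design, so only the baseline part of the noise is avoidable. The comparison is √(2s_t² + 4s_e²/3) against √(2s_t² + 2s_e²). The ratios are 1.22 at s_t = 0, 1.10 at s_e = s_t, and 1.04 at s_e = s_t/2.

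**Step 6: confidence intervals.** At a fixed number of patients, the width of the CI for mean change scales with the SD of change, so on average it widens by the same factors. It widens by less if the true change differs between patients, because that variation is common to both rules.

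**The case against.** The strongest reply is that the SAP never says that one tracing is used. An ECG assessment can be the triplicate set, with *last* picking the set nearest to dosing, and that is compatible with protocol 7.3.5. This stands to the extent that the single tracing is an inference. It does not remove the conflict, because the SAP lacks a rule for combining the set on either reading.

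Three stronger conclusions that a reader might draw are not supported:

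- **That SAP 7.5 also reduces post-dose triplicates to their last reading.** That rule concerns retests in by-visit summaries. Planned replicates about 2 minutes apart are not called retests anywhere, and SAP 17.5 plans no by-visit ECG summary. Using one reading on both sides would raise the ceiling to √3 = 1.73, but the text does not direct it.
- **That QTc change becomes much noisier.** The 41% figure holds only if nothing varies between time points except replicate noise, and no SD in the documents shows where the truth lies.
- **That the SAP's own outputs will contain false outliers.** SAP 17.5 only lists ECG data. The change and category tables are in protocol 7.3.5.1, whose parent section carries its own triplicate-mean baseline. The harm arises only if those tables are run with the SAP baseline.

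The last point also exposes a further gap: the SAP omits the QTc change analysis for a stated secondary objective. The separate PK plan might cover the concentration-QTc relationship, but neither document says so.

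**Conclusion.** The conflict is real and should be corrected before programming. If SAP 7.2 is implemented as one tracing, the SD of change in QTc on Cycle 1 Days 1 and 15 rises by at most 41%. It rises by about 4% to 12% where time-point variation equals or exceeds replicate variation (s_e equal to s_t, or half of it). False increases above 30 msec rise modestly, by up to 1.7 percentage points per comparison over the SDs tried, and only if the protocol 7.3.5.1 tables use this baseline. Increases above 60 msec are barely affected.

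These sizes rest on assumed SDs, independent normal components and no true drug effect. The direction depends only on replicate readings varying. The figures for Days 1 and 15 apply to the dose-escalation schedule. The expansion-stage schedule is in protocol Appendix 3, which was not in the text I could read, so its replicate scheme is unchecked.

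**What to change.** - **SAP 7.2:** replace the ECG sentence. Baseline for each ECG parameter is the mean of the available readings in the Cycle 1 Day 1 pre-dose triplicate.
- **SAP 17.5:** state that triplicate readings at a nominal time point are averaged before any summary or change is calculated, and that single ECGs are used as they are where the protocol schedules them.
- **SAP 7.5:** state that the retest rule does not apply to planned replicates.
- **SAP 17.5:** add the QTc change and category analyses of protocol 7.3.5, or name the document in which they are planned.

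The first three changes are wording only. The fourth needs table programming that the protocol already commits to. No new data are needed for dose escalation, where the triplicates are already scheduled. The expansion-stage schedule in Appendix 3 should be checked so that the averaging rule fits it.

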7.3. LAST KNOWN ALIVE DATE

For patients in FAS who are alive at the analysis cut-off date, the last known alive date will be derived based on the last date of the following recorded dates:

- All assessment / scan / sample collection dates (e.g. laboratory evaluation, vital sign assessment, physical examination, ECG, ECOG assessment, scan dates for tumor evaluation, etc.);
- Medication dates, including study drug, concomitant medications;
- Procedure dates;
- Date of subsequent anti-tumor therapy, including subsequent chemotherapy and oncology medication, surgery/procedure and radiotherapy;
- Adverse events start and end dates, date of change of CTCAE grade, SAE started date.

For subjects who are confirmed dead in the study, the last known alive date will also be derived according to the above rules, but this date will only be used as an alternative date to impute date of death if date of death is missing.

7.4. ON TREATMENT PERIOD AND WORST POST-BASELINE

For the analysis purpose, on treatment period is defined as the period from the day of first non-zero dose of treatment to 30 days after the last dose of treatment plus protocol window of 7 days (7-day window only applies for by-visit summaries) or the initiation of new antineoplastic therapy, whichever comes earlier.

Protocol Number: 2018-689-00US1 Page 19 of 43

The severity of adverse events and laboratory results depends on CTCAE grade. The worst post baseline value is defined as the highest CTCAE grade during on treatment period. The worst post-baseline abnormality is defined in the order of Abnormal, Clinically Significant (ACS) > Abnormal, Not Clinically Significant (ANCS) > Normal during the on-treatment period.

For numerical summaries, the worst post-baseline value is defined as the highest and/or the lowest numerical values.

7.5. RETESTS, UNSCHEDULED VISITS AND EARLY TERMINATION DATA

In general, for by-visit summaries, data recorded at the nominal visit will be presented. Unscheduled measurements will not be included in by-visit summaries but will contribute to the worst-case value where required (e.g. shift table).

In the case of a retest (same visit number assigned), the latest available measurement for that visit will be used for by-visit summaries.

Listings will include scheduled, unscheduled, retest visits, and early discontinuation data.

7.6. SUBGROUPS

Not applicable.

7.7. WINDOWING CONVENTIONS

No analysis visit windowing will be performed for this study. The planned visit windowing is presented in Appendix 1 of protocol amendment 5.

7.8. SOFTWARE VERSION

All analyses will be conducted using SAS Enterprise® Version 8.3 or higher version.

7.9. DATA HANDLING CONVENTIONS

Data will be summarized separately for stage 1 and 2: by dose level (Stage 1), and by malignancy type (Stage 2).

Continuous assessments will be summarized by number of patients (n), mean, standard deviation, median, minimum, and maximum. The decimal places for minimum and maximum will be the same as the max decimal places in original data. Mean and Median will keep one more decimal place than the decimal places in original data; standard deviation will keep 2 more decimal places than the decimal places in original data, but no more than 4 decimal

For categorical variables, descriptive statistics will include the number and percentage of patients for each category. The denominator for all percentages will be the number of patients

in that dose level or malignancy type within the population of interest, unless otherwise noted. The percentage will keep one decimal places. If the percentage is 100%, 100% will be reported; if the frequency is 0, no percentage will be reported. If needed, the 2-sided 95% confidence interval for percentage will be calculated using Clopper-Pearson method as well, and the decimal places will be the same as percentage.

7.10. MISSING DATA

In general, all available data will be included in the analyses. Unless otherwise specified there will be no substitution of missing data, i.e. missing data will not be replaced but will be handled as 'missing' in the statistical evaluation. Partial dates may be imputed for statistical analyses for specific outcomes. In such cases, the specific imputation rules are provided below. However, as a global convention, imputed dates should not be shown in listings.

Adverse Events

If the adverse event onset date is missing or partial, the date will be compared as far as possible with the date of first dose of study medication. Adverse events will be assumed to be treatment-emergent, unless there is clear evidence (through comparison of partial dates) to suggest that the adverse event stopped prior to the first dose of study medication or started more than 30 days after last dose of study medication or new antineoplastic therapy.

Missing or partial start dates:

- If the date has no missing year and month but the day is missing:
 - If the year and month of first dose date are the same as the year and month of the start date, then the date of first dose will be used.
 - Otherwise, 1st day of the month will be used.
- If the date has no missing year, but has missing month, and the year of first dose date
 is the same as the year of the start date, the date of first dose will be used.
- If the date has no missing year, but has missing month, and the year of first dose is not the same as the year of the start date, then January 1st will be used.
- If the start date is completely unknown, then use the date of first dose.

Missing or partial stop dates:

- If the date has no missing year and month but the day is missing, then use the last day of the month.
- If the date has no missing year, but has missing month, then use December 31st of that year.
- If the stop date is completely unknown, do not impute the stop date.

Note: If the imputed stop date is earlier than the start date, then the stop date is imputed with the start date. If the imputed start date is after non-imputed end date / SAE start date / date of change CTCAE grade then set start date to end date / SAE start date / date of

change CTCAE grade. For patients who died, if the imputed start/stop date is later than date of death, the imputed date will set to be date of death. If the imputed stop date is after the last known alive date, then the stop date is imputed with the last known alive date.

Concomitant Medications/Procedures

If concomitant medication starts and/or stops dates are missing or partial, the dates will be compared as far as possible with the date of first dose of study medication.

Medications will be assumed to be concomitant, unless there is clear evidence (through comparison of partial dates) to suggest that the medication stopped prior to the first dose of study medication or started later than 30 days after last dose of study drug. If there is clear evidence to suggest that the medication started prior to the first dose of study medication, the medication will be assumed to be Prior and Concomitant, unless there is clear evidence to suggest that the medication stopped prior to the first dose of study medication. If there is clear evidence to suggest that the medication stopped prior to the first dose of study medication, the medication will be assumed to be prior.

Missing or partial start dates:

- If the date has no missing year and month but the day is missing, 1st day of the month will be used.
- If the date has no missing year, but has missing month, then January 1st will be used.
- If the start date is completely unknown, do not impute the start date.

Missing or partial stop dates:

- If the date has no missing year and month but the day is missing, then use the last day of the month.
- If the date has no missing year, but has missing month, then use December 31st of that year.
- If the stop date is completely unknown, do not impute the stop date, and assign 'ongoing' status.

Note: If the imputed stop date is earlier than the start date, then the stop date is imputed with the start date. For patients who died, if the imputed start/stop date is later than date of death, the imputed date will set to be date of death. If the imputed stop date is after the last known alive date, then the stop date is imputed with the last known alive date.

Death Date

- If year and month of death date are known but the day is unknown, day will be imputed as 1st (for example, if a patient is reported to die on Dec 2017, the death date will be imputed as 1st Dec 2017).
- If only year are known, death date will be imputed as 1st Jan of the given year.
- If the imputed death date is prior to the last known alive date, then the death date

will be imputed as last known alive date+1.

If death date is totally missing, dates will be imputed as the last known alive date +
 1.

Note: if the imputed death date is after cut-off date, then the death date will be imputed as cut-off date.

Last known alive date

- If year and month are known but the day is unknown, day will be imputed as 1st.
- If only year is known, month and day would be imputed as Jan 1st.

Last dose date

Missing or partial date of last dose date of study treatment:

- If the date is partially missing, then impute the date as the last day of given part of
 original last dose date. If the day is missing, imputed date will be the last day of the
 month of the partial last dose. If the month is missing, imputed date will be the last
 day of the year of the partial last dose. If the imputed date is after the date of death
 (if the subject died) / last known alive date (if the subject is not known to die) / EOT
 date / EOS date, then it will be replaced with the earliest of the above.
- If the date is completely missing, then impute the earliest of the above.

Subsequent anti-cancer therapy

Missing or partial start date of anti-cancer therapy after end of study treatment:

- If the date has no missing year and month but the day is missing. And if the date has same year and month as last dose date, then equal to last dose date+1, else 15th day of the month will be used.
- If the date has no missing year, but has missing month, and the year of last dose date
 is the same as the year of the start date, the date of last dose+1 will be used.
- If the date has no missing year, but has missing month, and the year of last dose is before the year of the start date, then July 1st will be used.
- If the start date is completely unknown, then use the date of last dose+1.

Oncology Diagnosis History Dates

- If year is missing, do not impute.
- if year and month are known but the day is unknown, day will be imputed as 15.
- If only year is known, month and day would be imputed as July 1st.

Note: The imputed date will be compared to inform consent date. If it is later than the inform consent date, the incomplete date will be imputed as the inform consent date.

Date of Progression/ Date of Last Tumor Assessment

- If year and month are known but the day is unknown, day will be imputed as 1st.
- If both the day and month are missing or a date is complete missing, it will be considered as missing.

Prior oncology anti-cancer Medications

Missing or partial start dates:

- If the date has no missing year and month but the day is missing, 1st day of the month will be used.
- If the date has no missing year, but has missing month, then January 1st will be used.
- If the start date is completely unknown, do not impute the start date.

Missing or partial stop dates:

- If the date has no missing year and month but the day is missing, then use the last day of the month.
- If the date has no missing year, but has missing month, then use December 31st of that year.
- If the stop date is completely unknown, do not impute the stop date, and assign 'ongoing' status.

Note: If the imputed stop date is earlier than the start date, then the stop date is imputed with the start date. For patients who died, if the imputed start/stop date is later than date of death, the imputed date will set to be date of death. If the imputed stop date is after the last known alive date, then the stop date is imputed with the last known alive date.

Efficacy Analyses Data

Missing efficacy response will be treated as Not Evaluable (NE) at the visit.

